### 2.3 Regulatory Status in the United States

The PKG Movement Recording System was first FDA cleared on August 22, 2014 (K140086) and is intended to quantify kinematics of movement disorder symptoms in conditions such as Parkinson's disease, including tremor, bradykinesia and dyskinesia. Generation 2 PKG system 510(k) clearance was issued on September 20, 2016 (K161717) for Model: GKC-2000 (Gen 2) in which internal hardware to the logger was modified. Future generations of the PKG Movement Recording System will be cleared by the FDA through the regulatory approval process prior to being utilized in this clinical study. All commercially available versions of the PKG System and associated product instructions for use may be used in this study. The study is a post-market study and the system will be used within its FDA-cleared indication for use.

### 3.0 Subject Population

Approximately 350 subjects with Parkinson's Disease will be consented to provide 280 subjects followed through the initial 4-month follow-up period, which includes up to 20% attrition during this phase.

Subject selection criteria will include patients with PD who meet the following criteria. Subjects will be assessed in the ON state where applicable.

#### 3.1 Inclusion Criteria

**Study subjects must fulfill the following criteria:**

- Able and willing to sign a written informed consent for study participation
- Presumed levodopa responsive idiopathic Parkinson's Disease
- Age inclusive at the time of consent per PKG Indications for Use (46-83 years old)
- Has not been previously managed with the PKG

#### 3.2 Exclusion Criteria

**Subject with any of the following clinical criteria should be excluded:**

- Contraindication to increasing levodopa (e.g. orthostatic hypotension, hallucinations/psychosis or any other medical condition in the last year that would preclude increasing levodopa or other appropriate Parkinson's Disease medications)
- MoCA score <23 at screening visit
- Diagnosis of Essential Tremor
- Wheelchair bound or bedridden
- Currently utilizing or planning in the next 6 months advanced PD therapies (DBS, infusion, etc.)
- In the investigator's or sponsor's opinion, subject has any unstable or clinically significant condition that would impair the participant's ability to comply with study

requirements or interfere with interpretation of the study endpoints (e.g., subject unable to complete PKG watch wear instructions per Patient Instruction Manual)

Subjects will be assessed in the ON state where applicable.

## 4.0 Methods

### 4.1 Study Design Overview

The TARGET-PD RCT investigates the use of the PKG and standard of care in treating towards a target range compared to standard of care alone in the treatment of patients with uncontrolled Parkinson's disease. This is a prospective, multi-center, single-blind, randomized controlled study.

Each subject will be followed for 4 months after the baseline visit. All subjects in either group will have interim visits until they are considered to be controlled by the clinician per SOC (PKG-Group) or in the PKG based target range (i.e., controlled per expert review paper guidance in Pahwa et al., 2018) for the PKG+ Group. Interim visits may be conducted via telephone or in-office.

### 4.2 General Methods

#### *Protocol-Required Data Collection*

Protocol-required data collection at a given visit interval may be completed on one or multiple visit dates, if preferred by the institution as long as the testing is performed in compliance with protocol requirements and occurs within the corresponding visit window.

Data will be collected on study-specific case report forms (CRFs).

In the event inaccurate and/or incomplete PKG data collection occurs (e.g., subject wore PKG successfully but for less than the required duration, subject PKG Watch wrist band was not sufficiently secured creating PKG artifacts precluding interpretation, subject performed activities, such as the use of power tools, for a sufficient duration that interfered with PKG data collection, data collection completed when subject was OFF), data collection may be repeated one time. A note will be made in the case report form (CRF) that documents the reason for the repeated data collection and the initial and final test results will be recorded in the medical record. Only the final results will be recorded on the CRF.

#### *Parkinson's Disease Medication Use*

All subjects in the study will be asked to continue taking Parkinson's disease medication(s) as prescribed by their Parkinson's clinician throughout the duration of this study. Any modifications to medicines made during this study will be based on the clinician's judgment. Changes to medications will be recommended until the patient is considered to be controlled

unless contraindications are identified by the investigator. All PD medications and subsequent changes will be recorded in the medication log CRF. In addition, non-PD prescription medications of anti-depressants, anti-psychotics and blood pressure lowering agents will be tracked in the other medication log CRF.

#### *Timing of Clinical Visits*

Subjects will be asked to plan administration of Parkinson's medications to coincide with the time of each study-required clinic visit to ensure that in-clinic study evaluations occur when the subject is "ON" or believes they are achieving benefit from prescribed medications to standardize data collection for each patient and within the overall study cohort.

#### *PKG Watch Administration*

Study staff will be trained on the deployment and use of the PKG Watch to answer any patient questions and on the GKC ordering portal. The PKG Watch request will be entered into the GKC clinical portal. GKC will receive the order for the PKG Watch and send the PKG Watch to the patient for wear prior to the next study visit. The patient will return the PKG Watch to GKC and GKC will then upload the PKG including a summary of key findings for the study staff to download.

For both PKG+ Group and PKG- Group subjects, the PKG Watch will be programmed per standard commercial practices with the PD medication alert feature enabled (see Technical Instructions Manual). Subjects will be instructed to provide acknowledgement of PD medications taken by swiping the PKG Watch as described in the Patient Instruction Manual. The Patient Instruction Manual instructs patients to take PD medications as prescribed by their doctor.

The study staff will provide each subject with training on the use of the PKG Watch, a copy of the Patient Instruction Manual and complete the patient demonstration. Study staff will place the PKG Watch order in the Portal to allow GKC to deliver the PKG Watch to the subject. Once the subject has completed 6 full days of wear, the subject will return the PKG Watch to GKC. GKC will then download data from the PKG Watch per the instructions for use prior to the baseline visit. If, for any reason, the subject is unable to provide at least 6 full days of PKG data, the subject may have another PKG Watch programmed and dispensed for an additional wear period.

If at any time during the study, the subject is unable to successfully wear the PKG Watch or comply with study requirements, the subject may be exited from the study per Principal Investigator discretion.

[figure not shown]

Figure 2. Study Flow Chart

### 4.3 Screening Visit

Subjects that have not been treated previously with the PKG (i.e. PKG naïve) will be identified from routine clinical care, offered study participation, and provided a study informed consent document. Study goals and expectations will be discussed with subjects and all subject questions will be answered by a study Investigator and/or delegated designee. Subjects willing to participate will provide written informed consent.

Subject selection criteria will be documented. A Montreal Cognitive Assessment (MoCA) will be performed as part of selection criteria at the screening visit to exclude patients with dementia who are unlikely to be able to use the PKG independently. Only versions 7 or 8 of the MoCA will be used. Version and subform will be recorded in the screening visit CRF. Subjects who do not meet the study selection criteria will be documented as a screen failure on Subject Enrollment Logs in the Site Regulatory Binder and in the Electronic Data Capture system (EDC), as required. Eligible subjects will be assigned a Subject ID number and randomized using the EDC system in a 1:1 ratio to the PKG- Group (standard of care clinical assessments without use of PKG data) or the PKG+ Group (standard of care clinical assessments plus use of PKG data). Medical history and demographics will be collected on all patients after randomized into the study. The point of

enrollment into this study is when all selection criteria are met, an informed consent form is completed, and the randomization assignment has been completed.

A PKG Watch will be ordered through the GKC Portal and dispensed to the all subjects as previously described.

Screening and enrollment activities may be done remotely by phone or secure video conferencing (per existing site practices), as part of a routine clinic visit, as per local clinic and/or IRB requirements.

#### 4.4 Baseline Visit

At 28 days +/- 7 days (21-35 days) after the screening visit, subjects will return to the clinic for the Baseline Visit. For the PKG+ Group, the site staff will ensure the PKG Report is available prior to the Baseline Visit. A subject unable to wear a PKG Watch for at least 6 full days may be exited from the study (complete Study Completion Form) if they are unable to complete a repeat wear of the PKG Watch.

Subjects in both groups will undergo the routine clinical evaluation per standard of care. For all subjects, a medical history update, medication history, and an "ON" state neurological assessment will be completed. Protocol defined adverse events including falls, orthostatic hypotension, bothersome hallucinations, delirium, impairment that prohibits interaction with the PKG watch will be recorded. All subjects will also complete the PDQ-39 questionnaire and MDS-UPDRS. If the MDS-UPDRS is not considered part of the routine clinic visit, the MDS-UPDRS will be conducted for all visits by an independent certified rater.

For subjects in the PKG- Group (SOC control group), protocol required data collection will occur at the baseline visit. A Subject "ON" State Assessment will be completed and changes in medical history and medications will be recorded. The study investigator will complete the Clinician Assessment CRF to denote patient-reported symptoms, treatable findings, and clinical management planning based on his/her routine clinical assessment procedures. The study investigator will be blinded to the PKG information. In this group, the investigator will use clinical history and examination to determine if the subject is "controlled" or "uncontrolled" based on standard of care.

For subjects in the PKG+ Group, the study investigator will review and report on the PKG prior to the visit and use the information to guide the discussion with the subject during the clinical assessment. Subjects will remain blinded to their treatment group so direct reference to the PKG is to be avoided. The PKG will be used to determine if the subject is "controlled" or "uncontrolled" using the consensus-derived target ranges. PKG results will be recorded in the PKG Reporting CRF. The study investigator will complete the Clinician Assessment CRF to denote patient-reported symptoms, treatable findings, and clinical management planning based on his/her routine clinical assessment procedures along with the PKG information.

	Target Range
Bradykinesia Score (BKS)	Median BKS 23-25 and/or FDS > 7.5
Dyskinesia Score (DKS)	Median DKS 7-9 and FDS < 13

#### 4.5 Interim Follow-Up Visits

Interim follow-ups will be completed for subjects who are not considered to be controlled. For PKG- group subjects, controlled means per clinician standard of care assessment and for PKG+ group subjects, this is per the Acceptable Target Range:

	Target Range
Bradykinesia Score (BKS)	Median BKS 23-25 and/or FDS > 7.5
Dyskinesia Score (DKS)	Median DKS 7-9 and FDS < 13

Interim visits can be completed in-clinic or remotely via telephone per institutional requirements. This timeframe may vary depending on a variety of factors such as physician care practices, amount of total medication change needed, subject medication regimen compliance and subject tolerance to medication changes.

Approximately 28 days prior to each planned subject follow-up visit, a PKG Watch will be ordered through the GKC Portal and dispensed to each subject as previously described and PKG report obtained prior to the visit of PKG+ group subjects for investigator review.

For subjects in the PKG+ Group, the site staff will ensure the PKG is available prior to the Interim Follow-up Visit. Protocol required data collection will occur at each follow-up interim visit. A Subject "ON" State Assessment will be completed and changes in medical history and medications will be recorded. Any protocol defined AEs that have occurred will be captured on the AE Reporting CRF (see Section 8). The study investigator will review the PKG provided by GKC prior to the visit and use the information to guide the discussion with the subject during the clinical assessment. PKG results will be recorded in the PKG Reporting CRF. The study investigator will complete the Clinician Assessment CRF to denote patient-reported symptoms, treatable findings, and clinical management planning based on his/her routine clinical assessment procedures along with the PKG information.

For subjects in the PKG- Group, protocol required data collection will occur at each follow-up interim visit. A Subject "ON" State Assessment will be completed and changes in medical history and medications will be recorded. The study investigator will complete the Clinician Assessment CRF to denote patient-reported symptoms, treatable findings, and clinical management planning based on his/her routine clinical assessment procedures. The study investigator will be blinded to the PKG information during interim visits.

These steps will be repeated for each interim follow-up until the study subject is determined to be controlled or a maximum of the 4-month follow-up visit.

Up to 4 medication changes including at the Baseline visit and up to 3 interim visits will be allowed to get each subject into a “controlled” state. Interim follow-up visits end when PD symptoms have become optimized (considered controlled on oral therapies) per standard of care assessments for PKG- group subjects and per the Acceptable Target Range as published in Pahwa et al., 2018 and no further treatment changes are indicated as assessed by the study investigator and the subject will proceed to the next required study visit at 4-months Follow-Up.

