**TARGET-PD**

Study Visits	
 
• Screening
 
• Baseline (28 days +/- 7 days)
 
• Interim Visits (within approximately 21-35 days of previous visit)– investigators will be recommended to change medications until the patient is within the defined target range (PKG+ Group) or per investigator SOC assessments (PKG- Group); up to 3 interim visits allowed
 
• 4 months follow-up (120 days +/- 30 days)
 
• 1 year follow-up (12 months +/- 2 months)
 
• 2 year follow-up (24 months +/- 2 months)
 
• 3 year follow-up (36 months +/- 2 months)
 

---------------------	--

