#### **4.6 4-Month Follow-Up Visit**

All subjects will complete a follow-up visit approximately 4-months +/- 30 days (90-150 days) from the Baseline Visit.

Approximately 28 days prior to each planned subject follow-up, a PKG Watch will be ordered through the GKC Portal and dispensed to each subject as previously described. The site staff will ensure the PKG is available prior to the visit for the PKG+ Group.

Subjects in both groups will undergo the routine clinical work-up per standard of care. Protocol required data collection will occur at the visit. A Subject “ON” State Assessment will be completed and changes in medical history and medications will be recorded. Any protocol defined AEs that have occurred will be captured on the AE Reporting CRF (see Section 8). Subject surveys will be administered and include the PKG Patient Survey, PDQ-39, MDS-UPDRS, and MoCA. Medication changes (PD and other) will be updated in the corresponding medication log in the CRF.

For subjects in the PKG- Group (control group), the study investigator will complete the Clinician Assessment CRF to denote patient-reported symptoms, treatable findings, and clinical management planning based on his/her routine clinical assessment procedures. The study investigator will be blinded to the PKG information. In this group, the investigator will use clinical history and examination to determine if the subject is “controlled” or “uncontrolled.”

For the PKG+ Group, the site staff will ensure the PKG Report is available prior to the 4-Month Follow-Up Visit. A subject unable to wear a PKG Watch for at least 6 full days may be exited from the study (complete Study Completion Form) if they are unable to complete a repeat wear of the PKG Watch. The study investigator will review and report on the PKG prior to the visit and use the information to guide the discussion with the subject during the clinical assessment. The PKG will be used to determine if the subject is “controlled” or “uncontrolled.” PKG results will be recorded in the PKG Reporting CRF. The study investigator will complete the Clinician Assessment CRF to denote patient-reported symptoms, treatable findings, and clinical

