**TARGET-PD**

ICF	X				
Subject Selection Criteria	X				
Randomization	X				
Clinical Management Plans		X	X	X	X
PD and Other Medications	X	X	X	X	X
AE collection (protocol defined only)		X	X	X	X
PKG Scores (provided for PKG + Group)		X	X	X	X
MDS-UPDRS I, II, III, IV and Total Score		X		X	X
MoCA	X			X	X
PDQ-39		X		X	X
PKG Patient Survey				X	X

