## 10.0 Abbreviations and Definitions

AE	Adverse Event – Any untoward medical occurrence in a participant, which does not necessarily have a causal relationship with the trial intervention.
BKS	Bradykinesia Score – A score produced by PKG algorithms indicating symptoms of bradykinesia
DKS	Dyskinesia Score – A score produced by PKG algorithms indicating symptoms of dyskinesia.
FDS	Fluctuation Dyskinesia Score – A score produced by PKG algorithms indicating levels of fluctuation shown but interquartile ranges.
IQR	Interquartile Range - A measure of statistical dispersion, being equal to the difference between 75th and 25th percentiles.
LED	Levodopa Equivalent Dose – The comparison of levodopa with other medication regimes.
MoCA	Montreal Cognitive Assessment – A rapid screening instrument for mild cognitive dysfunction.
PD	Parkinson’s Disease – A progressive disease of the nervous system marked by tremor, muscular rigidity, and slow, imprecise movement, chiefly affecting middle-aged and elderly people. It is associated with degeneration of the basal ganglia of the brain and a deficiency of the neurotransmitter dopamine.
PDQ-39	Parkinson’s Disease Questionnaire – A 39 self-report questionnaire that assesses Parkinson’s disease-specific health related quality over the previous month.
PKG	Personal KinetiGraph - The output (including graphs, values, and curation) generated from the data captured on the PKG watch
PTI	Percent Time Immobile – Overall percentage of time the PKG detects that the patient is motionless.
PTT	Percent Time Tremor – Overall percentage of time the PKG detects that the patient experiences tremors.
PwP	People with Parkinson’s Disease
Target Ranges	Defined using Pahwa R, Isaacson SH, Torres-Russotto D, Nahab FB, Lynch PM, Kotschet KE. Role of the Personal KinetiGraph in the routine clinical assessment of Parkinson’s disease: Recommendations from an expert panel. Expert Review of Neurotherapeutics. 2018. DOI: 10.1080/14737175.2018.1503948.

	Target Range
Bradykinesia Score (BKS)	Median BKS 23-25 and/or FDS > 7.5

Dyskinesia Score (DKS)	Median DKS 7-9 and FDS < 13
-----------------------------------	-----------------------------

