The Parkinson's Disease Questionnaire will be completed by the patient at baseline, 4 months and annual follow-up visits concerning activities in the last month including self-care, walking ability, falling, mental stability, somnolence, etc. This a 5-point scale (never, occasionally, sometimes, often, always). A dimension score is calculated for each of 8 sections and a summary index is then calculated for the entire assessment.

4. Change in MDS-UPDRS Part I from baseline to 4 months

Change in MDS-UPDRS Part I and subsections as noted on the MDS-UPDRS data collection from baseline to 4 months.

Within-subject changes will be calculated as visit value minus baseline value such that a negative change reflects an improvement and positive change signifies a deterioration. Summaries of improved/same/worsened will be provided along with the continuous summaries.

5. Change in MDS-UPDRS Part II from baseline to 4 months

Change in MDS-UPDRS Part II and subsections as noted on the MDS-UPDRS data collection from baseline to 4 months.

Within-subject changes will be calculated as visit value minus baseline value such that a negative change reflects an improvement and positive change signifies a deterioration. Summaries of improved/same/worsened will be provided along with the continuous summaries.

6. Change in MDS-UPDRS Part IV from baseline to 4 months

Change in MDS-UPDRS Part IV and subsections as noted on the MDS-UPDRS data collection from baseline to 4 months.

Within-subject changes will be calculated as visit value minus baseline value such that a negative change reflects an improvement and positive change signifies a deterioration. Summaries of improved/same/worsened will be provided along with the continuous summaries.

7. Change in PKG Scores including BKS, DKS, PTT, FDS and PTI from baseline to 4 months

Change in PKG scores from baseline to interim1, interim 1 to interim2, interim 2 to interim3, interim3 to 4 months for those with interim visits conducted (uncontrolled) or baseline to 4 months for controlled.

Within-subject changes will be calculated as visit value minus baseline value such that a negative change reflects an improvement and positive change signifies a deterioration. Summaries of improved/same/worsened will be provided along with the continuous summaries.

PKG summary scores will be reported on the PKG at baseline, interims (if applicable for those uncontrolled), and 4 months including the following:

- Bradykinesia Score

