- Dyskinesia Score
- Fluctuation Score
- Percent Time Immobile (PTI)
- Percent Time Tremor Present (PTT)

Evaluation of individual patient and subgroup response from baseline assessed by change in PKG BK or DK scores from baseline to 4 months for controlled (in target range) and uncontrolled (out of target range) in PKG+ and PKG- groups

- Rate of subjects who were uncontrolled at baseline (PKG Summary Scores exceeded targets) and then became controlled at the 4-month visit (PKG Summary Scores reduced to below targets).
- Rate of subjects unresponsive to medication changes (i.e. no change to PKG BK scores with LED increase)
- Rate of subjects who required treatment changes but were unwilling to make changes (this group may not show any impacts to outcomes)
- Rate of subjects who required treatment changes but were contraindicated to make changes (this group may not show any impacts on outcomes)

8. Change in LED from baseline to each interim visit and 4 months

Calculation of Levodopa Equivalent Dose (LED) at each visit for each patient and a comparison of change in LED at each visit for each patient. If a change is made at the scheduled visit, the change is calculated for the next visit (e.g., a change at the BL visit means the subject has started taking the new medication/dose/frequency change the day after the BL visit, etc.) – See Appendix for reference in calculating LED.

Rate and change in PD medications including medication type, dosing, increase, decrease from baseline to interim1, interim2, interim3, and 4 months.

An analysis to look at medication change amount and frequency and impact on outcome of MDS-UPDRS and PKG BKS will be performed. Patients will be ranked by amount of LED change at each visit and grouped by number of times they had medication changes at a visit (e.g. 0, 1, 2 times, etc.) from baseline to the 4 month visit and correlated to the outcome of MDS-UPDRS and PKG score of BKS at 4 months.

- Rate of subjects who were marked as uncontrolled but had no medication changes will be noted.
- Rate of subjects who had medication changes but were less than 100mg LED will be noted.

9. PKG Patient Survey at 4 months

PKG Patient Survey at 4 months. Tabulate values and proportions and changes from baseline to each visit.

The rate at 4 months will be calculated for the PKG+ and PKG- groups for each section of the survey.

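### The protocol sets no minimum interval between the last medication change and the 4-month visit, so 4-month PDQ-39 and PKG results can partly reflect the previous dose

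*Protocol*

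**What the plan says.** **Number of changes.** Protocol 4.5: "Up to 4 medication changes including at the Baseline visit and up to 3 interim visits will be allowed". The interim steps repeat "until the study subject is determined to be controlled or a maximum of the 4-month follow-up visit".

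**Spacing.** The Study Visits row of the Protocol Summary gives "Interim Visits (within approximately 21-35 days of previous visit". This is written for interim visits only, and 4.5 adds that timing may vary with care practice, the size of the change and tolerance.

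**4-month visit.** Protocol 4.6: "All subjects will complete a follow-up visit approximately 4-months +/- 30 days (90-150 days) from the Baseline Visit". It is counted from baseline, not from the last change.

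**What is measured then.** In the Schedule of Events (Table 1), the row "MDS-UPDRS I, II, III, IV and Total Score" is marked at baseline, 4 months and the annual visits, but not at interims. PDQ-39 asks about "health related quality over the previous month" (Protocol 10.0); SAP 3.4 item 3 says it is completed "at baseline, 4 months and annual follow-up visits concerning activities in the last month". The PKG watch is ordered about 28 days before the visit (4.6), worn for 6 full days and returned to the sponsor for download (4.2).

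**LED dating.** SAP 3.4 item 8: "If a change is made at the scheduled visit, the change is calculated for the next visit". The new regimen is taken to start the day after the visit.

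Neither document states a stable-dose period before the 4-month visit or an analysis by time since last change.

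**The concern.** A change at baseline, interim 1 or interim 2 is normally followed by another interim about three to five weeks later. A change at interim 3 is followed by a visit whose date does not depend on it. The windows for interim 3 and the 4-month visit overlap on days 90-105.

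Two outcomes are exposed by the documents' own definitions. PDQ-39 looks back a month, so a shorter gap blends weeks on the old and new regimens. The 4-month PKG may be worn, wholly or partly, before the change, while the SAP assigns the increased LED to that visit.

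The second mismatch reaches named analyses. SAP 3.4 item 7 counts subjects as unresponsive when LED rises and the bradykinesia score does not move. It also counts those who pass from uncontrolled to controlled by 4 months. SAP 3.5 counts uncontrolled PKG+ subjects who could not be brought into range. A recording made before the last increase can put a subject on the wrong side of each count. Item 8 also correlates LED change with the 4-month bradykinesia score.

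**Working it through.** **Inputs.** Interim spacing 21-35 days (Protocol Summary); up to 3 interims (4.5); 4-month visit on day 90-150 (4.6); new dose from the day after the visit (SAP 3.4 item 8); PDQ-39 recall of one month, taken as 30 days (assumption); watch order about 28 days ahead (4.6); 6 full days of wear (4.2).

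**The plan's own figure.** 120 - 30 = 90 and 120 + 30 = 150, so the stated window reproduces.

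**Day of interim 3.** Sum of three gaps: 3 × 21 = 63 to 3 × 35 = 105; at 28-day spacing, 84.

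**Gap = 4-month visit day - interim 3 day.**
- 28-day spacing: day 120 gives 36; day 105 gives 21; day 90 gives 6.
- 35-day spacing: day 120 gives 15, the shortest gap possible at day 120 within the stated spacing.

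**PDQ-39.** A visit on day V recalls days V-30 to V-1. The new dose starts one day after interim 3, so recall lies wholly on it only if the gap is at least 31. Otherwise old-dose days = 31 - gap, up to 30.
- Gap 36: none. Gap 21: 10 of 30. Gap 15: 16 of 30. Gap 6: 25 of 30.

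**How often.** There are 15 × 15 × 15 = 3,375 combinations of three spacings. Each is paired with each window day that falls after interim 3, giving 202,002 schedules. All are weighted equally, which is an assumption and not a forecast.

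| 4-month visit | gap < 7 days | gap < 21 days | gap < 31 days |
|---|---|---|---|
| day 105 | 83/3,374 = 2.5% | 1,602/3,374 = 47.5% | 3,010/3,374 = 89.2% |
| day 112 | 0 | 560/3,375 = 16.6% | 2,105/3,375 = 62.4% |
| day 120 | 0 | 56/3,375 = 1.7% | 813/3,375 = 24.1% |
| day 136 or later | 0 | 0 | 0 |
| all days 90-150 | 8,147/202,002 = 4.0% | 46,878/202,002 = 23.2% | 80,502/202,002 = 39.9% |

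(At day 105, the one combination with interim 3 on that same day is left out.)

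**PKG.** If the gap is under 28 days, a watch ordered 28 days ahead is ordered before the change. Whether it is also worn before the change depends on shipping and return times, which the documents do not give. Assuming 3-10 days out and 3-7 days for return and report, a recording wholly on the new dose needs 3 + 6 + 3 = 12 to 10 + 6 + 7 = 23 days from an order placed at the change.

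**Does a 31-day minimum fit the window?** At the stated spacing, 105 + 31 = 136, inside day 150. The latest change that still fits is 150 - 31 = day 119. A change on day 120 gives 151, outside it. With a day-119 change and a day-150 visit, the watch order falls on 150 - 28 = day 122, after the change.

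**The case against.** The case against has force on several points.

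- *The nominal schedule has no conflict.* With 28-day spacing and a day-120 visit the gap is 36 days. Only subjects changed at interim 3 are exposed, and nobody can say from the documents how many there are. This stands.
- *A gap of only days is rare.* A reader might infer that 4-month outcomes will commonly be read within a week of a change. The table does not support that: none at day 120 or 112, and 4.0% over the window. Watch logistics also make visits days apart awkward, particularly in PKG+, where a report must be ready for each. This too stands, although logistics are not a rule and do not stop PDQ-39 from mixing doses at gaps of two to four weeks.
- *The spacing of other changes is soft as well*, since interim timing may vary. True, so the contrast with interim 3 is one of degree.
- *The primary endpoint is protected.* A reader might infer that MDS-UPDRS Total is compromised, or that benefit in PKG+ is understated. The documents do not support either. They give no time to effect for the scale, and assessment is in the ON state with dosing timed to the visit. The schedule is the same in both arms. The arms do define control differently (4.5), so the share reaching interim 3 could differ, but in which direction is unknown.
- *SAP item 8 is only a dating convention*, and it already groups subjects by number of changes. As a way to date LED it is sound. The difficulty arises only when that LED is set against a PKG worn before the dose began.

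**Conclusion.** The omission is real and modest in scope. As written, a subject changed at interim 3 may have a 4-month visit too soon for PDQ-39 to cover only the new dose, and too soon for the PKG to be sure of recording it. Given a change at interim 3, this concerns about 40% of permitted schedules for PDQ-39, or 24% when the visit is on day 120. Those figures rest on equal weighting of schedules, spacing within 21-35 days and a 30-day month.

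The supported harm is to PDQ-39 and to the PKG-based response and target-range rates. Any effect on MDS-UPDRS Total, and any direction by arm, is a possibility that the documents neither establish nor exclude. This is an inexpensive improvement to consider; it does not undermine the primary comparison.

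**What to change.** **Protocol 4.5 and 4.6, if the schedule is reused.** Hold the 4-month visit at least 31 days after the last PD medication change and within day 90-150. Allow no interim change after day 119. Require the 4-month PKG to be worn after that change. The day-119 limit has to be written down: because interim timing is flexible, the 31-day rule alone does not guarantee a visit inside the window. No extra visit or wider window is needed. The cost is that subjects changed late are seen later, so visit day may differ slightly by arm; report it by arm.

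**SAP 3.4 and 3.5, for the 41 enrolled.** The visit rule comes too late. Enrollment closed on 27 February 2020; 35 days to baseline plus 150 days puts the last in-window 4-month visit at about 30 August 2020, before the SAP's September date. What remains is to flag, or exclude, 4-month PKG recordings worn before the last dose change when computing the LED-response and target-range rates. Days from last change to the 4-month visit can be reported by arm. The work is one derived variable and one short table, provided the medication log holds change dates. With so few subjects, and a grouping formed after randomization, the days-since-change summary is descriptive and alters no main result; all subjects stay in the primary analysis.
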